After the screening evaluation, the study physician will review the study inclusion/exclusion criteria to determine if the participant is eligible for the study based on the screening materials. If the participant is eligible for the study, they will be given the consent form to read, and review with the consenting physician. The study consent will only be signed after all of the participant's questions are asked, and after all the risks and benefits are explained to and understood by the participant. Study related procedures will only be initiated after the consent form is signed by both the participant and consenting physician.

Indicate which of the following are employed as a part of screening or main study consent procedures

✓ Consent Form

Persons designated to discuss and document consent

Select the names of persons designated to obtain consent/assent

[name], MD

[name]

[name], MD

[name]

[name], MD

[name], MD

[name], MD

[name], MD

[name], MD

[name]

[name], MD

Type in the name(s) not found in the above list

Study Procedures

Describe the procedures required for this study

This is an open-label randomized outpatient trial to compare the safety and efficacy of two methods of transitioning patients off BUP. Opioid-dependent individuals who have successfully completed at least 6 months of BUP treatment and do not wish to remain in a long-term BUP maintenance will be screened for enrollment.

In the first stage (led-in phase) participants will be maintained on their usual dose of BUP (2-8 mg) at the research clinic for 1 month to assure that they are stable, compliant, and free from illicit opioids. Following that, participants will be randomly assigned to begin treatment with one of two regimens: 1) rapid BUP discontinuation and transition to XR-NTX, or 2) 5-week long BUP taper. Participants randomized to XR-NTX will receive a total of 3 injections. In both groups, participants will receive weekly individual therapy and monitoring for **3 months** post-randomization. During months 4-6 participants will be seen twice

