Evaluation of Depression and Anxiety symptoms: Participants who meet criteria for a Mood Disorder (MDD) of mild to moderate severity or an Anxiety Disorder will be followed closely during detoxification and subsequently. Mood and anxiety will be assessed both in therapy sessions and during MD visits. If a

patient demonstrates significant symptoms which persist following detoxification, we will offer the participant the option of beginning an antidepressant or an anti-anxiety treatment if deemed clinically warranted.

Managing controlled substances: Currently the study is run under the NYS Controlled Substance license # 0400081 held by the NYS OMH and the DEA Researcher Registration # PN0093461 held by the NYSPI Pharmacy Department. [name] has obtained his own NYS Controlled Substance license and a federal DEA research license. . The drug stock of controlled substances for each project will be ordered, maintained and prepared under the Institutional registration at the NYSPI Pharmacy (OMH/NYS Controlled Substance license # 0400081).

You can upload charts or diagrams if any

Criteria for Early Discontinuation

Criteria for Early Discontinuation

Drop out criteria during the study period include:

- 1) Development of serious psychiatric symptoms as indicated by the Clinical Global Impression (CGI) improvement score of 6 (much worse than baseline) or greater for 2 consecutive weeks or psychiatric or medical deterioration that cannot be managed safely in the context outpatient treatment offered at the study (in cases where the investigator determines that the participant needs immediate study discontinuation).
- 2) If the participant's continued opioid or other drug use places him/her at risk for self-destructive behavior or other harm as indicated by a CGI improvement score of 6 or more (much worse than baseline) for 2 consecutive weeks. In cases where the investigator determines that the participant needs immediate study discontinuation for continued opioid or other drug use, participants will be provided with referrals.
- 3) Development of serious medical condition(s) that may or may not be related to study participation as assessed by weekly visits with the psychiatrist, vital sign measurements, and weekly weight-ins.
- 4) If the participant becomes pregnant as assessed by monthly urine pregnancy testing
- 5) Ongoing non--adherence with recommended clinical visits, absence from study visits for 21 days.

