Patients who are exited from the trial for any reason will be offered continued treatment in the community unless a higher level of care is indicated (inpatient or residential treatment), or the patient requests treatment elsewhere, in which care help with arranging referrals will be offered. A clinic staff member, with physician backup, is available 24 hours per day by phone in case of emergency.

Participants may be removed from the trial if they repeatedly miss scheduled appointments or clinical

worsening necessitates more intensive treatment (drop out criteria are defined above). Subjects who develop serious psychiatric symptomatology (e.g., psychosis, suicidal ideation, severe depressive symptoms) during the study period will be dropped from the study and appropriate clinical referrals will be made. A patient who's continued opioid use places them at risk for self-destructive behavior or otherwise places them at significant risk will be discontinued from the study. This would include, but not be limited to, patients who become unconscious after using, engage in destructive or violent behavior while intoxicated, report driving while intoxicated, or develop medical complications from their opioid use. In all cases where subjects are discontinued from the study, the clinical research staff will assume clinical responsibility for the subjects until clinical referrals are operational.

In case that the patient is removed from the research trial for medical reasons, or is requesting withdrawal from the study, he/she will be retained in open treatment for the remaining study period. Upon removal of a patient from the trial due to clinical deterioration, the patient will be referred for appropriate follow-up treatment, in most instances either intensive outpatient or residential treatment. The PI or a study psychiatrist is available 24 hours/day by phone and/or beeper in case of emergency.

If a patient is discontinued from the study, or decides to withdraw, or relapses during study the participation, the patient will get treated with buprenorphine until they are linked with a referral for continuing buprenorphine treatment. Participants will receive a one-week supply of buprenorphine at a time during the transition process.

Blood and other Biological Samples

Please create or insert a table describing the proposed collection of blood or other biological specimens

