Systematic Assessment for Treatment and Emergent Events (SAFTEE): The SAFTEE as modified for Project COMBINE (Johnson et al., 2005) will be performed weekly, **and twice-monthly during study months 4-6** to identify any adverse symptoms. If participants report experiencing adverse symptoms since the previous visit, the research nurse will record the symptom as well as the date of onset, severity, and resolution (if applicable) and research psychiatrist will review it at least weekly and more frequently if symptoms are present.

Timeline Follow--Back (TLFB): The Timeline Followback method (Litten and Allen, 1992) will gather self-- reported opioid use data for each day during the month prior to study enrollment and each day during the study period. The TLFB confirmed by urine toxicology will be the primary outcome measure of psychoactive substance use and will be performed at **every study visit**.

Therapist Contact Log (TCL): The number and duration of treatment sessions will be documented by the therapist on a contact log.

End of Study Form (ESF): At study completion or the point of termination for patients who relapse or drop out, the research psychiatrist fills out an End of Study Form, which indicates whether or not a patient completed 25 weeks of treatment, the date of termination, the number of weeks of treatment completed from randomization to termination, and reasons for early termination, including documented relapse to opiates, resumption of buprenorphine maintenance, psychiatric worsening, medical worsening, or lost to follow--up.

Self--Report

Clinical Global Impression--Self (CGI--S): The CGI--Self is a two--item scale that asks the subject to rate his or her current level of symptoms and estimate changes from baseline (Guy, 1976). The CGI--S will serve as the primary self--reported measure of overall functioning.

Medical Outcomes Study--Sleep Scale (MOS--SS): The MOS--SM is a 12--item measure for characterizing the quality of sleep (Hays et al., 2005). Opioid withdrawal, both acute and protracted is characterized by insomnia and other sleep disturbances. The MOS--SM will be the primary outcome of sleep quality and length and will be collected at each visit.

Craving Scales-- Self: A visual analog scales is used for patients to rate the intensity of craving for opiates experienced since the previous visit ([name] et al., 2011).

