Any study of medication efficacy carries risk. However, the investigators have conducted a series of studies administering medications to patients with opioid use disorder. Further, [name] has specifically conducted a study at the clinic in which the outpatient method of rapid naltrexone induction was developed. Other clinic physicians have extensive experience in administering oral and injectable naltrexone to opioid--dependent patients as well as experience providing treatment with buprenorphine. Patients are seen weekly by a physician **until month 4, and twice-monthly during months 4-6** for evaluation of medication and side effects, medication compliance therapy, or dose adjustments or adverse effects, and for evaluation of safety and emergence of any safety related issues (e.g. pregnancy, clinical worsening including serious medical or psychiatric conditions, or worsening of substance use). Adverse Events and Serious Adverse Events will be carefully monitored during the study.

Relapse during outpatient naltrexone induction

During the detoxification phase of the study, particularly during washout day and during first few days when naltrexone is introduced if a patient resumes regular opiate use, then taking naltrexone, particularly naltrexone injection, may precipitate opiate withdrawal, which may be severe. Patients will be warned not to take the naltrexone if they resumed any level of opiate use, and opiate abstinence will be confirmed by urine toxicology prior to administering the next daily dose of naltrexone.

Psychiatric Monitoring and Removal from Study

Participants' mental and physical status is monitored weekly **until study month 4, and twice monthly during study months 4-6** by the physician. The psychiatrist will assess appropriateness for continuation in the research study on a continuous basis, and will remove from the trial patients with significant clinical deterioration or noncompliance of a type that could be dangerous. Although unlikely, it is possible that patients may become psychotic or depressed, requiring discontinuation of study medication, and possibly psychiatric intervention. The weekly monitoring of patients, along with ongoing evaluations with structured assessments, such as the Hamilton Depression Scale, should allow us to detect these psychiatric disturbances early and intervene appropriately.

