Contingency Management and Subject Compensation: Subjects will be encouraged to come for the clinical evaluations and for CBT sessions as described in this protocol. To minimize missed sessions, they will be reimbursed for transportation expenses, for providing data, and for time spent in completing study assessments in accordance with local site's IRB policies. Contingency management procedures which have been shown to successfully improve many behaviors ranging from medication compliance to adherence to protocol activities will be applied to this study. Subjects will earn chances at each visit to draw vouchers from a prize-bowl. A subject must complete all visit requirements to be able to draw vouchers at the end of a visit. If study medication is discontinued due to adverse events, subject will continue to draw vouchers based on the schedule below as long as they continue all other visit requirements are completed. Participants will earn one draw for each consecutive visit made, with a bonus 3 draws for every 3 consecutive weeks. If a participant misses a visit, their draws are reset. Each draw has a probabilistic chance of yielding one of four outcomes; an encouraging statement (e.g. 'good job'), a small prize valued at \$2.50, a large prize valued at \$20, or a jumbo prize valued at \$100. The probability of each particular outcome is fixed for every draw and is based on the relative number of slips for each prize category in the prize bowl. Using Petry et al.s (2005) framework each prize bowl will have 500 prize slips. 250 slips will be an encouraging statement (50% of the total slips), 209 will be for small prizes (41.8%), 40 slips will be for large prizes (8%), and 10 slips will be the jumbo prize (0.2%). Patients will earn 1 additional draw for every consecutive week of abstinence (all urine samples for a treatment week test negative). The increasing number of earned draws during the protocol follows the escalating incentive structure employed in other CM based treatments (Higgins et al., 1993). During the treatment (contingency management) subjects can earn up to **340** draws from the prize bowl if demonstrating 100% attendance during the 25 weeks of the protocol. Total earnings will vary depending on attendance. With an expected earning of \$2.85 per draw the maximum potential earnings for the CM for 25 weeks is **\$969**. However, actual observed earnings will be significantly less than the potential maximum due to attrition and missed visits.

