Study Aim #2: To determine whether treatment with XR-NTX reduces severity of protracted withdrawal seen following BUP discontinuation.

Significance testing and preliminary analysis:

All tests for main effects will be performed at two-tailed significance $\alpha=5\%$. We will examine all variables for outliers, the distributions of all continuous variables will be checked for normality and if needed transformations will be used before applying parametric techniques. The distribution of demographic variables and other covariate measures at baseline in the treatment arms will be examined (means, standard deviations, proportions and 95% confidence intervals). The analysis will be adjusted by three preselected covariates (primary opioid type, length of BUP maintenance, and average dose).

Primary Analyses

Subjects treated with XR-NTX will have significantly higher rates of successful transition off BUP at the end of study compared to subjects tapered off BUP. The effect of treatment on the primary outcome will be examined using logistic regression adjusted for specified covariates (primary opioid type, length of BUP maintenance, and average dose), and described using the estimated coefficients of the treatment term in the model, the corresponding odds ratios, and 95% confidence intervals.

Secondary Analyses

Longitudinal dichotomous and continuous outcomes will be modeled with generalized linear mixed effects models using appropriate link function (logit for dichotomous outcomes) with treatment, time, treatment by time interaction, and applicable baseline outcome measure as predictors. Time to relapse will be analyzed using survival analyses and Kaplan-Meier estimators. Dichotomous outcomes will be analyzed similarly to primary hypothesis with logistic regressions. The within subject correlation will be modeled using autoregressive AR(1) structure and random effects of subject. Significant time by treatment interaction indicates different change over time between treatment groups. If the interaction between time and treatment is not found to be significant, the interaction term will be omitted and an overall treatment effect will be tested.

D. QUALITY ASSURANCE

D1. Procedures in place to ensure the validity and integrity of the data

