Study Discontinuation

Criteria for removal from the study will include:

(1) substantial alcohol and other drug use that endangers the patient or requires a higher level of care such as inpatient or residential treatment; (2) psychiatric or medical deterioration that cannot be managed safely in the context outpatient treatment offered at the study clinics (e.g., acute suicide risk, acute medical problems); (3) Ongoing non-adherence with recommended clinical visits, absence from the clinic for more than 21 days; and (4) Pregnancy.

Patients who are exited from the trial for any reason will be offered a continued treatment in the community unless a higher level of care is indicated (inpatient or residential treatment), or the patient requests treatment elsewhere, in which care help with arranging referrals will be offered. Participants will be offer a weekly supply of buprenorphine for up to 30 days if they are being transitioned to another treatment program if they are removed from the trial. A clinic staff member, with physician backup, is available 24 hours per day by phone in case of emergency.

Participants may be removed from the trial if they repeatedly miss scheduled appointments or clinical worsening necessitates more intensive treatment (drop out criteria are defined above). Subjects who develop serious psychiatric symptomatology (e.g., psychosis, suicidal ideation, severe depressive symptoms) during the study period will be dropped from the study and appropriate clinical referrals will be made. A patient who's continued opioid use, places them at risk for self-destructive behavior or otherwise places them at significant risk will be discontinued from the study. This would include, but not be limited to, patients who become unconscious after using, engage in destructive or violent behavior while intoxicated, report driving while intoxicated, or develop medical complications from their opioid use. In all cases where subjects are discontinued from the study, the clinical research staff will assume clinical responsibility for the subjects until clinical referrals are operational.

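### The 21-day absence limit was not adjusted for the twice-monthly visits of months 4-6, so one missed visit can be enough to remove an abstinent participant before week 25, with no week-25 assessment set for that person.

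*Protocol*

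**What the plan says.** **Absence limit.** Criterion 5 in the protocol's Criteria for Early Discontinuation is "Ongoing non--adherence with recommended clinical visits, absence from study visits for 21 days". The same words return in the protocol's list of removal criteria under procedures for minimizing risks. SAP F3, Study Discontinuation, has "Ongoing non-adherence with recommended clinical visits, absence from the clinic for more than 21 days". None of the three varies the limit by study phase, and none says from which day the absence is counted.

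**Visit schedule.** Protocol, Study Procedures: "During months 4-6 participants will be seen twice" monthly. That is the only statement of the overall visit frequency for those months. The protocol is consistent with it elsewhere: physician monitoring is weekly "until study month 4, and twice monthly during study months 4-6", and the SAFTEE and BDI entries also change to twice monthly. Other text disagrees. The protocol's paragraph on outpatient study visits, the SAP's opening trial description (before A2) and SAP Table 1 keep weekly visits to the end, and SAP C1 says twice weekly.

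**Discretion.** Protocol, Criteria for Early Discontinuation: "Participants may be removed from the trial if they repeatedly miss scheduled appointments". SAP F3 has the same sentence.

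**After removal.** The End of Study Form is completed at study completion or at "the point of termination for patients who relapse or drop out, the research psychiatrist fills out an End of Study Form". Continued open treatment for the remaining study period is promised to people removed for medical reasons or asking to withdraw, not to those removed for absence. The Locator Form is meant to help find drop-outs for follow-up, but no week-25 assessment of them is set out.

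**Analysis.** SAP C3: "The effect of treatment on the primary outcome will be examined using logistic regression adjusted for specified covariates". It does not say how a participant who left before week 25 is classed.

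**The concern.** A 21-day limit suits weekly visits: one missed visit leaves 14 days, and it takes two in a row to reach 21. At twice-monthly spacing one missed visit already passes it. Months 4-6 are the run-up to the primary outcome, which is status at week 25. The rule can therefore end observation of someone who is off buprenorphine and abstinent, for a reason that says little about either.

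The protocol expects some misses: it notes that "actual observed earnings will be significantly less than the potential maximum due to attrition and missed visits". If removed participants are then counted as failures, the arm with more successes has more of them to lose. Equal miss rates in the two arms would still shrink the difference and the odds ratio, and the 95% confidence interval for that odds ratio is the study's stated purpose (SAP A4). If removed participants are left out instead, fewer than the planned 25 per arm are analysed.

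**Working it through.** **1. Gap between attended visits.** After k consecutive missed visits the gap is (k + 1) × spacing.

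| Spacing | 1 missed | 2 missed | 3 missed |
|---|---|---|---|
| 7 days | 14 | 21 | 28 |
| 14 days | 28 | 42 | 56 |

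At 14 days one miss exceeds both the protocol's limit (21) and the SAP's (more than 21). At 7 days the protocol's limit needs two misses in a row and the SAP's needs three. All of this counts from the last attended visit. Counted from the missed visit, someone who misses one and comes to the next has been absent 14 days and never meets the limit.

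**2. The plan's own figure.** SAP A4: 25 per arm, 40% against 77% success, two-sided 5%, 80% power. Full enumeration of two binomials with the uncorrected chi-square test gives 80.5%, so the figure reproduces. The planned odds ratio is (0.77/0.23)/(0.40/0.60) = 5.02.

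**3. Upper-bound illustration.** These are assumptions, not document figures:
- five twice-monthly visits before the endpoint (weeks 15, 17, 19, 21 and 23);
- each is missed, and not made up within 7 days, with probability p, independently and equally in both arms and whatever the participant's true status;
- the rule is always applied;
- removed participants count as failures.

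Share meeting the rule: f = 1 − (1 − p)^5. Success rates become 0.77(1 − f) and 0.40(1 − f).

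| p | f | XR-NTX v taper | Difference | Odds ratio | Power |
|---|---|---|---|---|---|
| 0 | 0 | 77.0% v 40.0% | 37.0 points | 5.02 | 80.5% |
| 2% | 9.6% | 69.6% v 36.2% | 33.4 points | 4.04 | 72% |
| 5% | 22.6% | 59.6% v 31.0% | 28.6 points | 3.29 | 58% |
| 10% | 41.0% | 45.5% v 23.6% | 21.8 points | 2.70 | 39% |

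The 10% row only shows the range; no weight is put on it.

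In whole people, 19 v 10 successes of 25 (odds ratio 4.75, 95% CI 1.41 to 16.05) becomes 17 v 9 at 2% (3.78, 1.17 to 12.19) or 15 v 8 at 5% (3.19, 1.00 to 10.17). These are unadjusted odds ratios with Wald intervals; SAP C3 adjusts for three covariates.

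**4. Removed participants left out.** Under the same assumptions the expected difference stays at 37 points. The number per arm is 25(1 − f) = 22.6 at 2% or 19.3 at 5%. With 23 or 19 per arm, power is 75% or 68%.

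**5. Two consecutive misses required.** The chance of at least one run of two in five visits is 1 − [q^5 + 5pq^4 + 6p²q³ + p³q²], with q = 1 − p. It is 0.2%, 1.0% or 3.7% at p = 2%, 5% or 10%. Even if all of these are counted as failures, the difference is 36.9, 36.6 or 35.6 points.

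**6. No effect.** If the rule is not applied to single misses, or if leavers are found and classed by their week-25 status, the 37 points are unchanged.

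**The case against.** The strongest reply is that the text works against removal after one miss. The criterion opens with the word *ongoing*, and the discretionary sentence speaks of people who miss appointments *repeatedly*. One missed visit followed by a return is neither. If two misses in a row are what the sponsor means, step 5 shows that almost nothing is lost. Attendance is also supported by transport reimbursement and by prize draws that reset after a missed visit, so miss rates may be low. The trial is an exploratory pilot, and the SAP says its power figures serve only to support the proposal.

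Most of this stands, and it limits the size of the point. It does not remove it. The day from which absence is counted is undefined, the 21 days is the only number staff are given, and that number fits a schedule which the protocol's Study Procedures does not use in months 4-6. An exploratory aim does not help either, since the quantity at risk is the odds ratio and interval meant to inform a larger trial.

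Three stronger readings are tempting and not supported:
- *One missed visit leads to removal.* The wording makes it possible, not automatic.
- *Staff would apply the rule differently by arm.* The trial is open-label and the choice is theirs, but nothing in the documents suggests they would.
- *Buprenorphine supplied at exit turns an abstinent leaver into a failure.* One exit sentence is worded broadly, but SAP F3 describes a weekly supply as an offer to people moving to another programme. No effect is claimed from it.

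**Conclusion.** The mismatch is in the current text and is certain: the limit is shorter than the gap left by one missed twice-monthly visit, counted from the last attended visit. It is also certain that no week-25 assessment is set for someone removed for absence.

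The size is uncertain. It depends on how staff use their discretion, on a miss rate that the documents do not give, and on how leavers are classed. The range is from no effect to a fall from 37 points to 33.4 (2% missed) or 28.6 (5% missed). The lower figures need the rule to be applied every time and every removed participant to be counted as a failure, so they are a bound and not a forecast. Under the weekly schedule that still stands in parts of both documents the problem largely disappears, which is why the schedule and the limit should be settled together. This is a worthwhile, inexpensive correction; it does not by itself make the trial's result unreliable.

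**What to change.** 1. **Tie the limit to the schedule.** In both protocol removal lists and in SAP F3, keep 21 days while visits are weekly. In months 4-6 require two consecutive missed visits, the second not made up within 7 days: 14 + 14 + 7 = 35 days since the last attended visit. State that days count from the last attended visit. Attempt contact after the first missed visit, as the protocol already does for a missed injection, so that safety contact is not delayed.
2. **State one visit schedule for months 4-6** in the protocol's outpatient visits paragraph, the SAP's opening trial description, SAP C1 (now twice weekly) and SAP Table 1.
3. **Separate removal from outcome collection.** State that removal for absence ends study visits but not the primary outcome. Seek every randomised participant for a week-25 urine and TLFB, using the Locator Form. In SAP C3, analyse all randomised participants by that status, count unknown status as failure, and add one sensitivity analysis that varies the number of unknowns counted as successes in each arm.

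Cost: one sentence in each of the three removal lists, an aligned schedule in four places, and two or three sentences in SAP C3. No new instrument is needed. The downside is somewhat later formal removal in months 4-6 and a few extra contact attempts.
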